Extended Study Protocol

Title:

Lidocaine-Adrenaline-Tetracaine gel (LAT gel) vs lidocaine infiltration as local anesthesia for suturing a superficial wound: a comparative study in adults.

Investigators:

- [name]
- Prof dr. [name]
- [name]

Sponsor:

Vrije Universiteit Brussel

Introduction

UZ Brussel has a busy emergency department where patients are triaged upon arrival. Depending on the pathology, they are referred to urgent care (internal medicine pathology), trauma care (orthopedic and surgical emergencies), or pediatric care (pediatric emergencies). Patients presenting with wounds requiring suturing are frequently triaged to the trauma care unit.

At UZ Brussel, the standard local anesthesia for suturing a wound in adults is always an infiltration anesthetic (such as lidocaine). However, other (topical) treatments exist. For example, LAT gel is used in children at UZ Brussel.

Adult patients frequently complain about the additional pain caused by the lidocaine injection. Moreover, it has previously been described that the injection can make the technical procedure of suturing more difficult. Additionally, the increased risk of needle-stick injuries argues against lidocaine injection.

In children, LAT gel has been implemented precisely for these reasons. Studies also show that the additional pain caused by injections increases the risk of developing needle anxiety. Furthermore, the technical procedure of applying LAT gel in a restless and anxious child is much easier than administering a lidocaine injection.

LAT gel consists of lidocaine 4% (80 mg), adrenaline 0.1% (2 mg), tetracaine 0.5% (10 mg), and hypromellose gel. It is a gel that can be prepared magistally and sterily by the pharmacy in a 2 mL syringe with a Luer cap. It should be stored in the refrigerator to maintain optimal consistency and to achieve a shelf life of three months. The gel is not classified as a narcotic, therefore a prescription for narcotic substances is not required.

Ernst et al. (1) already investigated the difference in pain experience between LAT gel and lidocaine injection in 1997. Vandamme et al. (2) wrote a similar article but with a retrospective study design. Adler et al. (3) also compared LAT gel with placebo. All three studies conclude that LAT gel is at least equivalent to lidocaine infiltration. The literature regarding the use of LAT gel in children is much more extensive and justifies its standard use in pediatric patients.

Objective

The objective of this study is to document and compare the pain experience of a patient requiring suturing between anesthesia with LAT gel and anesthesia with lidocaine infiltration.

This study could therefore provide an indication of which form of local anesthesia in adults is preferable in terms of pain experience, both during administration of the anesthetic and during suturing.

Hypothesis (H1):

LAT gel results in less severe pain during administration, during testing of the anesthesia, and during suturing compared with lidocaine infiltration.

Hypothesis (H2):

LAT gel results in more severe pain during administration, during testing of the anesthesia, and during suturing compared with lidocaine infiltration.

Null hypothesis (H0)

LAT gel results in a similar pain experience during administration, testing of anesthesia, and suturing compared with lidocaine infiltration.

Department Involved in the Study

Emergency Department, UZ Brussel

[name]

[name]

Belgium

Prof. dr. [name]: Supervisor en promotor.

Methods

Study design

Comparative prospective monocentric study.

Materials

- **Electronic Medical Record: Emergency report**
- **2 mL LAT gel (4% lidocaine, 1:1000 epinephrine, 0.5% tetracaine) per patient in the LAT gel group – treatment option**
- **Maximum 4.5 mg/kg 1% lidocaine per patient or maximum 7 mg/kg 1% lidocaine with epinephrine per patient – treatment option**
- **Suturing materials as described in the hospital protocol**
- **Linear Visual Analogue Scale (VAS)**
- **Ruler**
- **Physician data collection form**

Study Population

Inclusion Criteria:

- Adults
- Wounds ≤ 7 cm
- Wounds suitable for single-layer closure
- No mucosal involvement or wounds in the direct vicinity of mucosa

Exclusion Criteria:

- Age < 18 years
- Suspected nerve injury
- Suspected tendon injury
- Wounds located on the genitalia, nose, or ears
- Substance intoxication
- Substance abuse
- Additional sedation with nitrous oxide (NO)
- Pregnancy
- Glaucoma
- Allergy to the described anesthetic agents or preservatives
- Wounds older than 8 hours
- Contaminated wounds
- History of cardiac disease
- History of respiratory disease
- Altered mental status
- Inability to use or interpret the visual analogue scale
- Inability to experience or report pain

Target Population Size:

50–100 selected patients presenting to the Emergency Department of UZ Brussel. Patients will be selected according to the predefined inclusion and exclusion criteria. Study period: September 2020 – February 2022 (maximum). Based on estimates from 2018 data at UZ Brussel (approximately 1800 sutures per year), the required data could likely be collected within 1–2 months.

Procedure

All selected patients will be treated by the attending physician for their open wound. Based on the physician's treatment plan, the patient will be assigned to either the LAT gel group or the lidocaine group. Pain during administration of the anesthetic will be recorded by the treating physician using a Visual Analogue Scale (VAS). Immediately after patient contact, the physician will complete additional information regarding patient and wound characteristics on a data collection form prepared by the researchers. In the lidocaine group, lidocaine infiltration will be administered immediately before suturing. A VAS score will also be obtained and documented on the designated form. After 30 minutes (LAT gel group) or 5 minutes (lidocaine infiltration group), the effectiveness of the anesthesia will be assessed using a 25G needle prick, and documented by the treating physician using the VAS. If the anesthesia is insufficient, additional lidocaine infiltration will be administered and documented on the same form. If sufficient anesthesia is achieved, the treating physician will suture the wound according to the UZ Brussel hospital protocol. During suturing, pain experience will again be assessed using a VAS and recorded on the form together with the physician's observations regarding the characteristics of the suturing procedure. Further data analysis will be performed by the investigators.

*Analysis**Primary analysis*

The first analysis will determine whether LAT gel reduces pain experience compared with lidocaine infiltration, specifically during:

- Administration of the anesthetic
- Testing of the anesthesia
- Suturing

Sub-analyses:

The following aspects will also be analyzed:

- Wound Characteristics
 - o Length and location (skull, face, fingers, toes, lower limb, upper limb, trunk)
- Suturing Characteristics
 - o Number of sutures
 - o Duration of suturing
 - o Suturing technique (sutures, staples, glue, other)
- Patient Characteristics
 - o Age
 - o Seks
 - o Weight
- Medication
 - o Dose of LAT gel
 - o Dose of lidocaine
 - o (+ additional doses if required)

Statistical Analysis Plan:

Data entry will be performed in Excel.

Further statistical processing will be performed in SPSS using ANCOVA.

Publication Policy / Agreements:

- **Thesis:** [name], supervisor [name], co-supervisor [name]
- **Poster and presentation:** [name], supervisor/[name], co-supervisor [name]
- **Scientific article:** [name] – [name]– [name]

Referenties

Short Study Protocol

Title

Lidocaine–adrenaline–tetracaine gel (LAT gel) vs lidocaine infiltration as local anesthesia for suturing a superficial wound: a comparative study in adults.

Brief Description of the Proposed Content

Problem Statement

UZ Brussel has a busy emergency department where patients are triaged into urgent care, trauma care, and pediatric care. Trauma care frequently treats patients with wounds requiring suturing. At UZ Brussel, the standard local anesthesia for suturing wounds in adults is infiltration anesthesia with lidocaine. However, other (topical) treatments exist. In children at UZ Brussel, LAT gel is already used. Adult patients frequently complain about the additional pain caused by lidocaine injection. Moreover, the injection has been described as making the technical act of suturing more difficult. The increased risk of needle–stick injuries is another disadvantage. In children, LAT gel has been implemented precisely because of this pain complaint. Studies also show that injection pain increases the risk of needle phobia. Furthermore, applying LAT gel in an anxious or restless child is technically easier than administering a lidocaine injection.

Short Description:

The study could therefore provide an indication of which form of local anesthesia in adults is preferable with regard to pain experience during administration of the anesthetic and during suturing.

Method

All selected patients will be treated by the attending physician for their open wound. Based on the physician's treatment plan, the patient will be assigned to either the LAT gel group or the lidocaine group. Pain during anesthetic administration will be recorded by the physician using a Visual Analogue Scale (VAS). Immediately after patient contact, the physician will complete additional data regarding patient and wound characteristics on a form prepared by the investigators. In the lidocaine group, lidocaine infiltration will be administered just before suturing, and a VAS score will also be recorded. After 30 minutes (LAT gel group) or 5 minutes (lidocaine infiltration group), the effectiveness of anesthesia will be tested using a 25G needle prick and documented using a VAS. If anesthesia is insufficient, additional lidocaine infiltration will be administered and recorded. If anesthesia is adequate, the physician will suture the wound according to the hospital protocol. Pain during suturing will again be assessed using the VAS and recorded together with the physician's observations. Further analysis will be performed by the investigators.

Study population

At least 70 selected patients presenting to the Emergency Department of UZ Brussel. Patients will be selected using the predefined inclusion and exclusion criteria. Study period: September 2020 – February 2022. The number of patients was calculated based on internal data and a power calculation.

Improvement Pathway

If the hypothesis is confirmed, lidocaine infiltration could potentially be replaced by LAT gel application for specific indications (based on the study's inclusion and exclusion criteria).

Lidocaine infiltration could then serve as an alternative or additional local anesthetic, with the aim of reducing patient pain experience.

Intended objective

Hypothesis (H1): LAT gel results in less severe pain during administration, testing of anesthesia, and suturing compared with lidocaine infiltration.

Sub-analysis:

- Wound characteristics
- Suturing characteristics
- Patient characteristics
- Need for additional lidocaine administration

Flow chart

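### The treating physician chooses the anaesthetic and no adjustment covariates are named, so the LAT-versus-lidocaine comparison is at risk of confounding by indication, of unknown size and direction

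*Combined protocol and SAP*

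**What the plan says.** The Extended Study Protocol (Methods, Study design) calls the study a "Comparative prospective monocentric study". Its Procedure section and the Method section of the Short Study Protocol share the same allocation sentence: "Based on the physician's treatment plan, the patient will be assigned to either the LAT gel group or the lidocaine group". The text of neither describes a random sequence, concealment, matching, stratification or a propensity method. The flow chart is not shown and is not held against the plan.

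On usual care, the Extended Study Protocol's Introduction states that "the standard local anesthesia for suturing a wound in adults is always an infiltration anesthetic".

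On analysis, the Statistical Analysis Plan says: "Further statistical processing will be performed in SPSS using ANCOVA". It names no covariates. The Analysis section asks whether LAT gel reduces pain at administration, at testing and at suturing. Wound factors ("Length and location (skull, face, fingers, toes, lower limb, upper limb, trunk") and age, sex and weight appear separately under Sub-analyses, in one list with number of sutures, duration, technique and doses. On timing: "Immediately after patient contact, the physician will complete additional information regarding patient and wound characteristics on a data collection form".

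On use of the result, the Improvement Pathway in the Short Study Protocol says: "If the hypothesis is confirmed, lidocaine infiltration could potentially be replaced by LAT gel application for specific indications".

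**The concern.** H1 and the primary question are causal: they ask what LAT gel does to pain. A causal reading needs groups that would have had similar pain under the same anaesthetic. Here the physician decides who gets which, and the default is infiltration, so a patient receives LAT gel because something about the wound, the patient or the physician prompted it. If that something also affects pain, the VAS scores can differ with no treatment effect, or a real effect can be hidden. The same physician also sutures the wound and records the VAS, so personal preference and skill may travel with the treatment.

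The three pain scores are not equally exposed. Administration pain follows fairly directly from injection versus gel. Needle-prick and suturing pain depend more on the wound and the patient, and are more vulnerable. At stake is whether a difference at those two points could justify LAT gel in place of infiltration.

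**Working it through.** **1. Does the plan give a figure to reproduce?** Not on confounding. The only related figure is the Short Study Protocol's total of at least 70 patients (the Extended Study Protocol gives 50–100). It is attributed to a power calculation whose inputs are not stated, so it cannot be reproduced. I take N = 70. As a yardstick, assuming 1:1, two-sided 5% and 80% power, the detectable difference is (1.960 + 0.842) × √(4/70) = 2.802 × 0.239 = 0.67 SD.

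**2. Which listed variables could serve for adjustment?**

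- Set before the choice: wound length, location, age, sex, weight.
- Set at or after the choice: number of sutures, duration, technique, doses. These are not baseline confounders.
- Not listed: baseline pain, wound depth, reason for choosing the anaesthetic.

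The form is completed after patient contact, so even the first group is recorded once treatment and pain scores are known.

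**3. What does a given bias do to the test?** With no true effect, bias b in SD units, 1:1 allocation and SE = √(4/N), the two-sided 5% false-positive rate is 1 − Φ(1.96 − b/SE) + Φ(−1.96 − b/SE). For N = 70, SE = 0.239.

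| Bias b (SD) | b/SE | False positives, N = 70 |
|---|---|---|
| 0 | 0 | 5.0% |
| 0.1 | 0.42 | 7.0% |
| 0.2 | 0.84 | 13.3% |
| 0.3 | 1.26 | 24.1% |
| 0.5 | 2.09 | 55.2% |

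A bias of 0.3 SD arises, for example, if a binary wound factor worth 1 SD of VAS differs in prevalence by 30 percentage points between groups (0.30 × 1 = 0.3). At that bias the rate is 18.6% for N = 50 and 32.3% for N = 100, so a larger sample makes the error worse.

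**4. Illustration in millimetres.** All inputs are assumed: severity S ~ N(0,1); P(LAT) = 1/(1 + exp(ln(OR) × S)); VAS = 30 + g × S + error, total SD 20 mm; N = 70; no true effect. The last column adjusts for a recorded measure that correlates 0.7 with S.

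| OR per SD of severity | g (correlation with VAS) | Unadjusted: spurious difference, false positives | Adjusted, imperfect measure |
|---|---|---|---|
| 2 | 6 mm (6/20 = 0.3) | about 4 mm, 12% | about 2 mm, 7% |
| 3 | 8 mm (8/20 = 0.4) | about 7 mm, 32% | about 4 mm, 13% |
| 4 | 10 mm (10/20 = 0.5) | about 10 mm, 57% | about 6 mm, 22–23% |

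Adjusting for S itself, measured without error, brings the bias to about 0 and the error to about 5%. With about a quarter of patients on LAT gel, unadjusted false positives are about 10% to 51%. For scale, 0.67 SD at an SD of 20 mm is 0.67 × 20 = 13.4 mm, so a spurious 4–10 mm is 30% to 75% of the difference that 70 patients could detect (4/13.4 and 10/13.4).

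**The case against.** The best defence is that the plan already contains a safeguard. ANCOVA implies covariates, and the main wound and patient factors are collected. A reader might infer from the Sub-analyses heading that the primary comparison will be unadjusted. The documents do not say that; they leave the covariates unnamed. This stands: the unadjusted figures describe an analysis the plan does not specify. But a model with no named covariates, fed from a list that mixes pre- and post-choice variables, cannot be relied on to remove confounding by indication.

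Second, eligibility narrows the case mix: wounds up to 7 cm, single-layer closure, no contamination, no suspected nerve or tendon injury, no altered mental status. This helps, but length within that limit, seven locations and patient factors can still differ between groups.

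Third, a reader might infer that LAT gel will go to the easier wounds and so be flattered. No selection rule in the documents supports that. Selection could run the other way, for instance if needle-anxious patients are given the gel. This stands, and neither size nor direction can be claimed.

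Fourth, a reader might take the Improvement Pathway as a planned change of practice. Its wording is conditional and limited to specific indications, and the Objective promises only an indication of which method is preferable. This stands too, although H1 and the primary question remain causal in wording.

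**Conclusion.** The concern holds as a risk built into the design. Physician's choice, a causal hypothesis and an ANCOVA without named covariates together mean that the plan, followed as written, can yield a biased LAT effect. Needle-prick and suturing VAS are the most exposed and administration pain less so. H1, and the possible replacement of infiltration, therefore lack adequate support.

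The size is illustrative only: about 4–10 mm and 12–57% false positives unadjusted, and about 2–6 mm and 7–23% after adjustment for a measure correlating 0.7 with true severity. These figures rest on an assumed SD of 20 mm, assumed odds ratios of 2 to 4, assumed severity–pain correlations of 0.3 to 0.5, and N = 70. They are not estimates of this study's error rate.

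A reader might also infer that adjustment would restore validity. It does so only if the recorded covariates capture the whole confounder without error. With baseline pain, wound depth and reason for choice not listed, the documents give no ground for that. Allocation also cannot be repaired after enrolment, so the point should be settled before recruitment.

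**What to change.** **Preferred.** In the Procedure section and in the Short Study Protocol's Method section, replace the allocation sentence with concealed 1:1 randomisation: sequentially numbered opaque sealed envelopes, opened only after eligibility is confirmed, in permuted blocks stratified by skull/face versus limb/trunk. The cost is the envelopes, an ethics and consent amendment, and the physicians' loss of free choice for study patients. It needs no extra patients or visits. The Extended Study Protocol estimates about 1800 sutures a year and likely collection within 1–2 months, so recruitment looks feasible. One set of eligibility criteria covers both options; the sponsor should confirm that every eligible patient could receive either. Randomisation does not blind the pain scoring.

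**If physician's choice stays:**

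- State that the study is observational.
- Make the primary analysis an ANCOVA adjusted only for pre-treatment factors: wound length, location grouped into a few categories (seven are too many for 50–100 patients), age and sex.
- Exclude number of sutures, duration, technique and doses as covariates.
- Record the pre-treatment factors and the reason for choice before the anaesthetic is given.
- Report an association with residual confounding, and remove the replacement claim from the Improvement Pathway.

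This costs SAP wording, an edit to the Short Study Protocol, and a small change to the procedure and form. It reduces the bias but does not remove it.

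### Systemic analgesia is not listed for collection or adjustment, although two of the three primary pain scores follow unequal waits (30 vs 5 minutes); any resulting bias has unknown size and direction

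*Combined protocol and SAP*

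**What the plan says.** The primary analysis in the Extended Study Protocol compares pain at three moments: administration of the anaesthetic, testing of the anaesthesia, and suturing. On the second, the Procedure section says "After 30 minutes (LAT gel group) or 5 minutes (lidocaine infiltration group), the effectiveness of the anesthesia will be assessed using a 25G needle prick". The Method section of the Short Study Protocol gives the same two times. For the lidocaine group the Procedure section adds: "In the lidocaine group, lidocaine infiltration will be administered immediately before suturing". Neither protocol fixes a time from arrival to the anaesthetic in either group.

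Of the 17 exclusion criteria, the only analgesic or sedative co-treatment named is nitrous oxide sedation. Entries such as "Substance intoxication", altered mental status and inability to report pain do not describe ordinary therapeutic analgesia.

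The Medication variables under Sub-analyses are "Dose of LAT gel", the lidocaine dose, and "additional doses if required". On the form, the Procedure section says that "the physician will complete additional information regarding patient and wound characteristics on a data collection form prepared by the researchers"; the form itself is not reproduced. The emergency report is listed under Materials, but nothing is said about extracting analgesics from it.

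Allocation follows the physician's treatment plan. The Statistical Analysis Plan names ANCOVA in SPSS and no covariates.

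**The concern.** A systemic analgesic acts on the same outcome as the local anaesthetic. If one is given at about the time the local anaesthetic is applied and is still taking effect, a LAT patient is scored 25 minutes further into its action than a lidocaine patient. The plan would credit that difference to LAT gel. Randomised allocation would balance how many patients receive an analgesic, but it would not equalise the wait before the score. Here allocation is by physician's choice, so use itself may differ as well.

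The testing and suturing scores are exposed to the unequal wait; the administration score is not. An ANCOVA cannot adjust for a variable that was never collected. The result matters because the Short Study Protocol (Improvement Pathway) says that, if the hypothesis is confirmed, LAT could replace infiltration for specific indications.

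**Working it through.** The plan gives no figure on this point to reproduce. The only exact quantity is the difference in waits: 30 − 5 = **25 minutes**.

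**Does the 25 minutes become a bias?** The documents give neither the share of patients who receive an analgesic nor its effect, so this is an illustration with assumed inputs:

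- pL, pC: share given an analgesic in the LAT and lidocaine groups
- aL, aC: minutes by which the analgesic precedes the local anaesthetic
- E: full analgesic effect, 10 to 20 mm on a 100 mm VAS
- T: minutes to full effect, 30 to 60, with linear onset f(t) = min(t/T, 1)

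Bias toward LAT at the prick test = pL × E × f(30 + aL) − pC × E × f(5 + aC).

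| Scenario | Bias toward LAT |
|---|---|
| (a) Equal use of 10–50%, given when the anaesthetic is applied | 0.4 to 8.3 mm |
| (b) Equal use, given 25 min earlier relative to the anaesthetic in the lidocaine group | 0 mm |
| (c) Equal use, given 60 min before the anaesthetic in both groups | 0 mm |
| (d) Use of 10% (LAT) vs 60% (lidocaine), given 15 min before | −1.25 to −6.0 mm |

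End points:

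- (a) low, T = 60: 0.10 × 10 × (30/60 − 5/60) = 0.42 mm. High, T = 30: 0.50 × 20 × (1 − 5/30) = 8.33 mm.
- (b) f(30) − f(5 + 25) = 0.
- (c) both groups are already at full effect, so the difference is 0.
- (d) T = 60, E = 10: 0.10 × 10 × 45/60 − 0.60 × 10 × 20/60 = 0.75 − 2.00 = −1.25 mm. T = 30, E = 20: 0.10 × 20 × 1 − 0.60 × 20 × 20/30 = 2 − 8 = −6.0 mm.

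The sign depends on use and timing, and the documents give neither. Scenario (b) cannot be ruled out, because infiltration is tied to suturing and not to arrival.

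**What would a yes/no covariate remove?** It addresses unequal use. It does not address unequal time of action. Take the upper case of (a), with equal group sizes and the analgesic counted as given before the anaesthetic. Users differ by 20 × (1 − 5/30) = 16.67 mm between groups and non-users by 0. The adjusted difference is 0.50 × 16.67 + 0.50 × 0 = 8.33 mm, the same as without adjustment. Clock times are needed as well.

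**What would restriction to unexposed patients cost?** Assume the minimum of 70 patients splits into 35 per group and the SD is 25 mm. The 95% half-width is 1.96 × 25 × √(2/35) = 11.7 mm. With assumed use of 30–60%, 35 × 0.70 = 24.5 (say 24) to 35 × 0.40 = 14 patients per group remain. The half-widths are then 1.96 × 25 × √(2/24) = 14.1 mm and 1.96 × 25 × √(2/14) = 18.5 mm.

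**The case against.** A reader might infer that the schedule biases the comparison in favour of LAT by a stated number of millimetres. The documents do not support that. The 25 minutes run from the local anaesthetic, not from an analgesic dose. For a drug taken before arrival or at triage, the interval to the lidocaine group's test is unspecified. With physician-chosen allocation, use may differ either way. The documents do not say that any systemic analgesic is given, or that patients waiting for LAT to work are more likely to receive one. If the local anaesthetic works, scores may be too low to fall much further, and the additional lidocaine given when anaesthesia is insufficient further limits the effect on suturing scores. All of this stands.

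A reader might also infer that analgesic use will go unrecorded. That is too flat: the form is not shown and the emergency report is a listed source. What can be said is that its collection and adjustment are not planned in the text.

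It can further be argued that the objective is the patient's pain experience under two approaches, so the LAT wait is part of what is compared. That is a legitimate reading, but it does not cover differences in analgesic use that arise from who was chosen for which treatment. Even under that reading, describing co-treatment by group is needed to interpret the result.

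**Conclusion.** The point holds as a gap in data collection and adjustment, not as a demonstrated bias toward LAT. Systemic analgesia other than nitrous oxide sedation is neither excluded nor listed for collection or adjustment. Allocation is not randomised, and the testing and suturing scores follow waits that differ by 25 minutes. An unmeasured co-intervention could therefore confound two of the three primary comparisons. Carry-over would be the wrong name for it, since this is not a crossover design.

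The bias may favour LAT if use and timing relative to the anaesthetic are similar in both groups; otherwise it may be nil or reversed. The millimetre figures rest wholly on assumed use, effect and onset, and serve only to show that the sign is undetermined. Without drug and clock times nobody could tell afterwards which case applied. This is a cheap improvement worth making, not a ground for rejecting the comparison.

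**What to change.** - **Record.** Add to the physician form any systemic analgesic or sedative before or during the visit, with drug, dose and clock time, checked against the emergency report. Add the clock times of anaesthetic administration, prick test and first suture.
- **Describe.** Report analgesic use, and the time from analgesic to each VAS score, by group.
- **Adjust.** Name analgesic use before the study anaesthetic as a covariate in the ANCOVA for the testing and suturing scores.
- **Support.** As sensitivity analyses only, repeat both comparisons (i) taking the time from analgesic to score into account, and (ii) in patients with no analgesic before the study anaesthetic. Report analgesics given during the wait descriptively. Do not restrict on them, because they arise after treatment has started and LAT patients have longer in which to receive one.
- **Interpret.** Do not make the conclusion depend on the main and sensitivity analyses agreeing. Agreement would be undefined, and the restricted analysis could fail through imprecision alone.

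The cost is a few more form fields and one or two model terms. No change to patient care is proposed.

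### No VAS is specified for the supplementary lidocaine injection, and no rule says how rescued patients enter the administration and suturing comparisons

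*Combined protocol and SAP*

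**What the plan says.** The Procedure section of the Extended Study Protocol fixes the order of events. The treating physician records a VAS when the assigned anaesthetic is given. Then: "After 30 minutes (LAT gel group) or 5 minutes (lidocaine infiltration group), the effectiveness of the anesthesia will be assessed using a 25G needle prick", also scored by VAS. Then: "If the anesthesia is insufficient, additional lidocaine infiltration will be administered and documented on the same form". The rule is not limited to one group. Next: "If sufficient anesthesia is achieved, the treating physician will suture the wound according to the UZ Brussel hospital protocol". Last: "During suturing, pain experience will again be assessed using a VAS and recorded on the form". The Method section of the Short Study Protocol repeats this sequence.

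The primary analysis covers three scores: "The first analysis will determine whether LAT gel reduces pain experience compared with lidocaine infiltration, specifically during" administration, testing and suturing.

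Rescue appears in the analysis only at a lower level. The Extended Study Protocol lists it among the medication sub-analyses ("additional doses if required"), and the Short Study Protocol lists it as a sub-analysis ("Need for additional lidocaine administration"). The Statistical Analysis Plan consists of data entry in Excel and ANCOVA in SPSS. It says nothing about patients who received supplementary lidocaine.

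**The concern.** The supplementary drug is the comparator, and it is given before suturing pain is scored. A LAT patient whose gel fails is therefore sutured after lidocaine infiltration, but nothing moves that score out of the LAT group. The same patient has had the injection that LAT is meant to spare, yet the only administration score the text calls for is the one for the gel.

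The two groups are not affected alike. A rescued infiltration patient gets more of the same drug and already has an injection score. A rescued LAT patient gets the other group's drug and has no injection score.

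The Objective says the preferred anaesthetic will be judged on pain at administration and at suturing, which are the two affected scores. The Improvement Pathway of the Short Study Protocol says a confirmed hypothesis could lead to LAT replacing infiltration for specific indications. With no rule in place, rescued patients could be kept as observed, dropped or moved to the other group once the data are known.

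**Working it through.** **Figures in the plan.** The documents give no rescue rate, VAS standard deviation or effect size, so the plan has no figure of its own to reproduce on this point. The minimum of 70 patients (Short Study Protocol, Study population) is said to rest on a power calculation, but its inputs are not given. It is used here only to set 35 per group (70/2, equal split assumed).

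**From the documents.** The order is administration VAS, test VAS, rescue if needed, suturing VAS. Rescue is possible in both groups.

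**Assumed, for illustration only.** 100 mm VAS; gel application 5 mm, injection 35 mm; LAT rescue proportion pL from 10% to 40%; infiltration rescue proportion pC of 5%; SD 25 mm; two-sided 5% test.

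**1. Administration, highest score per patient, ignoring rescue after infiltration.**
- Recorded difference: 5 − 35 = −30 mm.
- Counting rescue injections in a proportion f of LAT patients: (1 − f)×5 + f×35 − 35 = −30×(1 − f).
- f = 10%, 20%, 30%, 40% gives −27, −24, −21, −18 mm.

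**2. Allowing rescue in both groups.** Let R be the unscored pain of a rescue injection and D the fall in suturing VAS that rescue produces, each taken as 30 mm and equal in both groups. The shift toward LAT is (pL − pC)×R for administration and (pL − pC)×D for suturing. With SE = 25×√(2/35) = 5.98 mm, the chance of a significant result when the true difference is zero is 1 − Φ(1.96 − shift/SE) + Φ(−1.96 − shift/SE).

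| LAT rescue (pC = 5%) | Shift toward LAT | Chance of significance |
|---|---|---|
| 10% | 0.05×30 = 1.5 mm | about 6% |
| 20% | 0.15×30 = 4.5 mm | about 12% |
| 30% | 0.25×30 = 7.5 mm | about 24% |
| 40% | 0.35×30 = 10.5 mm | about 42% |

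The sign depends on the rescue rates. With pL = pC the shift is 0. With pL = 5% and pC = 20% it is (0.05 − 0.20)×30 = −4.5 mm, that is, against LAT.

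**3. Suturing, a second illustration.** Take 50 mm if anaesthesia fails and is not rescued, and 10 mm if it is adequate or rescued.
- Without rescue at 30% LAT failure: 0.70×10 + 0.30×50 = 22 mm for LAT.
- Infiltration at 5% failure: 0.95×10 + 0.05×50 = 12 mm. The difference is 10 mm against LAT.
- After rescue: 10 versus 10, difference 0. Dropping rescued patients also gives 10 versus 10.
- At 20% and 40% LAT failure the differences before rescue are 18 − 12 = 6 mm and 26 − 12 = 14 mm. Both also become 0.

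This measures the shift against a hypothetical in which failed anaesthesia is not supplemented. The procedure does not plan that.

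**4. Testing.** The needle-prick VAS is taken before rescue in both groups, so rescue cannot alter it.

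**The case against.** A reader might infer that the plan is biased toward LAT. The documents do not show this. Rescue applies to both groups and no failure rates are given, so the direction depends on the rates and on how much rescue changes the scores in each group. Allocation follows the physician's treatment plan, which adds confounding of unknown direction. The net bias cannot be signed.

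A reader might also infer that rescue pain is never scored. The text says the extra infiltration is documented on the form, but the form is not among the documents and the flow chart is not shown. The wording on administration pain is not expressly confined to the first administration. What stands is that no VAS is specified for that injection.

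Nor are LAT failures hidden. The testing VAS is a primary comparison and should reflect inadequate anaesthesia, and need for rescue is sub-analysed. Neither, however, corrects the administration and suturing comparisons.

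The strongest objection is that the suturing score after rescue may be the intended measure. The Improvement Pathway foresees lidocaine as a back-up or supplement to LAT, and for that strategy an as-observed suturing VAS is legitimate. This stands, and it is why the score should be kept and labelled. It does not rescue the administration score, because a LAT-with-back-up strategy still has to count the back-up injection's pain.

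The illustrations also have limits. The suturing example ends at no difference, not at LAT superiority, and the administration benefit never reverses. The administration example in step 1 adds nothing for rescued infiltration patients, whose highest score could also rise.

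**Conclusion.** The point holds as a gap in measurement and analysis rules, not as a demonstrated bias. Followed as written, the plan counts a rescued LAT patient as LAT with an administration score that omits an injection and a suturing score obtained after the comparator drug. If rescue is more frequent after LAT, with similar effects of rescue in both groups, both comparisons shift toward LAT.

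Every millimetre figure above rests on assumed inputs. They show that the effect could be small (1.5 mm at 10% LAT rescue) or material (10.5 mm at 40%), and that it vanishes at equal rescue rates. This should be fixed, and it is a cheap improvement. It is more than missing detail, because injection pain that is not recorded at the time cannot be recovered later.

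**What to change.** Leave the clinical rescue rule unchanged. Change the form and the Statistical Analysis Plan as follows.

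1. Add a VAS line to the form for any supplementary infiltration, in either group.
2. Define administration pain per patient over all anaesthetic administrations, initial and supplementary (for example the highest VAS), analysed by first treatment.
3. Keep suturing VAS as observed, by first treatment, and label it as including lidocaine rescue. Add a sensitivity analysis giving rescued patients in both groups the worst rank. Worst rank should not be the main analysis: it would replace the planned ANCOVA and make the result depend on an open-label judgement of insufficiency for which no VAS threshold is stated.
4. Report the between-group difference in rescue proportion with a 95% CI beside the primary results.

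The cost is one extra VAS line and a few sentences of analysis text. The downside is that LAT's apparent administration benefit may be smaller.
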